## 8.3 Recording of Adverse Events

At each contact with the subject, the investigator must seek information on adverse events by specific questioning and, as appropriate, by examination. Information on all adverse events should be recorded immediately in the source document, and also in the appropriate adverse event module of the case report form (CRF). All clearly related signs, symptoms, and abnormal diagnostic procedures results should be recorded in the source document, though should be grouped under one diagnosis.

All adverse events occurring during the study period and for a minimum of 100 days after the last dose of nivolumab and 90 days after the last dose of ipilimumab must be recorded. Following the subject's written informed consent to participate in the study, all AEs and SAEs, whether related or not related to study drug, are to be continuously collected, including those thought to be associated with protocol-specified procedures. The investigator should report any SAE occurring after these aforementioned time periods, which is believed to be related to study drug or protocol-specified procedure.

The clinical course of each event should be followed until resolution, stabilization, or until it has been determined that the study treatment or participation is not the cause. Serious adverse events that are still ongoing at the end of the study period must be followed up to determine the final outcome. Any serious adverse event that occurs after the study period and is considered to be possibly related to the study treatment or study participation should be recorded and reported immediately.

Non-serious AEs should be followed to resolution or stabilization, or reported as SAEs if they become serious. Follow-up is also required for non-serious AEs that cause interruption or discontinuation of study drug and for those present at the end of study treatment as appropriate.

CONFIDENTIAL

This material is the property of the NYU School of Medicine. Do not disclose or use except as authorized in writing by the study sponsor

## **8.4 Reporting of Serious Adverse Events and Unanticipated Problems**

The investigator (or designee) will seek information on AEs at each patient contact, and record all AEs that occur from the time the informed consent is signed until 30 days after the end of study treatment. CTCAE version 4.03 terms should be used.

All AEs after initiation of study treatment and until 30 days after the last study treatment, regardless of relationship to study treatment, will be reported. Additionally, any SAE or other AE of concern that the investigator believes may be related to study treatment and that occurs later than 30 days after last study treatment should be reported. Information for any nonserious AE that starts during the treatment period or within 30 days after last treatment will be collected from the time of the event until resolution of the event, or until the patient's last study visit, whichever comes first. Serious adverse event information will be collected until the event is considered chronic and/or stable.

Study treatment includes nivolumab, ipilimumab and radiation therapy.

Investigators and the protocol sponsor must conform to the adverse event reporting timelines, formats and requirements of the various entities to which they are responsible, but at a minimum those events that must be reported are those that are:

- related to study participation,
- unexpected, and
- serious or involve risks to subjects or others (see definitions, section 8.1).

Note: Immediately reportable criteria must be reported to the IRB at each annual review.

Serious adverse event reporting will begin in conjunction with the date of informed consent. Any SAEs occurring prior to study drug administration that the investigator believes may have been caused by a protocol procedure must be reported immediately to the Sponsor or its designee and recorded on the case report form.

All fatal or life-threatening adverse events must be immediately reported to the Sponsor by telephone or e-mail. Within 24 hours of the event, the Serious Adverse Event (SAE) Form supplied by NYUSoM must be faxed to the Sponsor (Overall PI), who must then inform the NYUSoM IRB, PCC CTO, and DSMC within 24 hours of the event whether full information regarding the event is known or not. Additional follow-up by the investigator will be required if complete information is not known. De-identified source documentation of all examinations, diagnostic procedures, etc. which were completed with respect to the event should be included with the SAE form. Care should be taken to ensure that the patient's identity is protected and the patient's identifiers (as assigned at the time of study enrollment) are properly mentioned on any copy of source document provided to the Sponsor. For laboratory results, include the laboratory normal ranges.

In case of accidental or intentional overdose of study drug (nivolumab and/or ipilimumab), even if asymptomatic or not fulfilling a seriousness criterion, the overdose is to be reported to the Sponsor immediately (within 1 working day) using the AE and SAE forms supplied by NYUSoM. Overdose of study drug is defined in Section 8.1.

All serious adverse events (SAEs) will be evaluated by the DSMC. If meeting the requirements for expedited reporting, the Sponsor will report the adverse event to all regulatory authorities with jurisdiction over ongoing trials with the study drug and to all other investigators involved in clinical trials with the study drug. The investigator is responsible for reporting all SAEs to the appropriate IRB, DSMC, and FDA.

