## **6.2 Dose Delay and Discontinuation Criteria**

### **6.2.1 Immune-Related Adverse Events (irAEs)**

Special attention must be paid to adverse events (AEs) that may be suggestive of a potential immune-mediated pathophysiology. Since inhibition of immune checkpoints stimulates the immune system, immune-mediated adverse events may occur.

Immune-related adverse events (irAEs) are AEs of immune nature (i.e., inflammatory) in the absence of a clear alternative etiology. Immune-mediated AEs are specific events (that include pneumonitis, diarrhea/colitis, hepatitis, nephritis/renal dysfunction, rash, and endocrine [adrenal insufficiency, hypothyroidism/thyroiditis, hyperthyroidism, diabetes mellitus, and hypophysitis]) for which subjects received immunosuppressive medication for treatment of the event, with the exception of endocrine events (hypothyroidism/thyroiditis, hyperthyroidism, hypophysitis, diabetes mellitus, adrenal insufficiency), which are included regardless of treatment since these events are often managed without immunosuppression.

IrAEs include events, regardless of causality, occurring within 100 days of the last dose. IrAEs are limited to subjects who received immunosuppressive medication for treatment of the event, with the exception of endocrine events (hypothyroidism/thyroiditis, hyperthyroidism, hypophysitis, diabetes mellitus, adrenal insufficiency), which are included regardless of treatment since these events are often managed without immunosuppression.

An irAE can occur shortly after the first dose or several months after the last dose of treatment. All AEs of unknown etiology associated with drug exposure should be evaluated to determine possible immune etiology. If an irAE is suspected, efforts should be made to rule out neoplastic, infectious, metabolic, toxin or other etiologic causes. Subjects who develop a Grade 2 or higher irAE should be discussed immediately with the overall Principal Investigator.

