#### **6.8.1 Adverse Event Follow-up Post-Treatment:**

All participants will be followed until resolution or stabilization of any serious or reportable adverse events occurring during treatment or starting within 30 days of last study drug. Assessments may continue for ongoing reportable adverse events. Participants removed from protocol therapy for unacceptable adverse events will be following until resolution or stabilization of the adverse event.

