##### **Initial Report: within 24 hours of awareness of the event:**

The following events must be reported to the study sponsor by telephone within 24 hours of awareness of the event:

- Unanticipated problems related to study participation,
- Serious adverse events, regardless of whether they are unexpected.
- Overdose of Study Drug, defined in Section 8.1.
- Pregnancy: Although pregnancy is not considered an AE, it is the responsibility of the investigator to report to the Sponsor (or designee), by telephone within 24 hours of identification, any pregnancy occurring in a female subject or female partner of a male subject, during the study or within 5 months after the last dose of study drug for a female subject or within 7 months after the last dose of study drug for a male subject. Any complication of pregnancy affecting a female subject or female partner of a male subject, and/or fetus and/or newborn must be reported as an SAE. All pregnancy outcomes will be followed as described in Section 8.1. Pregnancies must also be reported on a Pregnancy Surveillance Form to BMS immediately as described in Section 8.1.
- Exposure during Pregnancy or Breastfeeding (even if not associated with an adverse event)
- Occupational exposure (even if not associated with an adverse event)
- Potential drug-induced liver injury (DILI): These events are considered important medical events and should be reported as SAEs. See Section 8.1 for DILI definition.

In the event the investigator is informed of an SAE that occurs after 30 days after the last dose of study treatment, only those SAEs or other AEs of concern deemed by the investigator to be related to study treatment will be reported to the sponsor. The investigator should make every effort to obtain follow-up information on the outcome of a treatment-related SAE until the event is considered chronic and/or stable.

Additionally, an **FDA Form 3500 (MEDWATCH Form)** must be completed by the investigator and faxed to the study **Sponsor/Overall PI** within 24 hours. The investigator shall maintain a copy of the MEDWATCH Form on file at the study site or can be obtained from the FDA website:  
<http://www.fda.gov/safety/medwatch/howtoreport/downloadforms/default.htm>.

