#### **8.4.5 Sponsor Reporting: Notifying BMS**

SAEs, whether related or not related to study drug, and pregnancies must be reported by the Sponsor/Overall PI to BMS within 24 hours of awareness of the event. SAEs must be recorded on BMS or an approved form; pregnancies must be reported on a Pregnancy Surveillance Form.

SAEs that occur following the subject's written consent to participate in the study through 100 days of the last dose of nivolumab and 90 days of the last dose of ipilimumab must be reported by the Sponsor to BMS Worldwide Safety, whether related or not related to study drug. If applicable, SAEs must be collected that relate to any later protocol-specified procedure (e.g., a follow-up biopsy).

Following the subject's written consent to participate in the study and for a minimum of 100 days of the last dose of nivolumab and 90 days of the last dose of ipilimumab, all AEs SAEs, whether related or not related to study drug, are collected, including those thought to be associated with protocol-specified procedures. The investigator should report any SAE occurring after these aforementioned time periods, which is believed to be related to study drug or protocol-specified procedure.

CONFIDENTIAL

This material is the property of the NYU School of Medicine. Do not disclose or use except as authorized in writing by the study sponsor

An SAE report should be completed for any event where doubt exists regarding its seriousness;

If only limited information is initially available, follow-up reports are required. (Note: Follow-up SAE reports should include the same investigator term(s) initially reported.)

If an ongoing SAE changes in its intensity or relationship to study drug or if new information becomes available, a follow-up SAE report should be sent by the Sponsor within 24 hours to BMS (or designee) using the same procedure used for transmitting the initial SAE report.

Non-serious Adverse Events (AE) will be provided by the Sponsor to BMS in aggregate via interim or final study reports as specified in the agreement or, if a regulatory requirement [eg, IND US trial] as part of an annual reporting requirement.

BMS Reporting Contacts:

**SAE Email Address:** [contact]

**SAE [contact]

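### Two incompatible adverse-event windows (30 days versus 100/90 days after treatment) leave unrelated SAEs and some late immune-related events open to non-collection

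*Combined protocol and SAP*

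**What the plan says.** The shorter window is in Section 8.4. The investigator is to "record all AEs that occur from the time the informed consent is signed until 30 days after the end of study treatment", and "All AEs after initiation of study treatment and until 30 days after the last study treatment, regardless of relationship to study treatment, will be reported". Beyond that point 8.4 adds only "any SAE or other AE of concern that the investigator believes may be related to study treatment and that occurs later than 30 days" (counted from the last study treatment). Section 8.4.1 is restrictive about SAEs learned of after day 30: "only those SAEs or other AEs of concern deemed by the investigator to be related to study treatment will be reported to the sponsor".

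The longer window is in several places. Section 8.3 says that AEs on study plus those arising "for a minimum of 100 days after the last dose of nivolumab and 90 days after the last dose of ipilimumab must be recorded", related or not. Section 8.1 (Adverse Event Reporting Period) sets the same minimum for AEs and SAEs, again regardless of relationship, and says they are to be reported under Section 8.4. Footnote 11 of both schedules monitors AEs to 100 and 90 days. In Section 8.4.5, SAEs through 100 and 90 days "must be reported by the Sponsor to BMS Worldwide Safety, whether related or not related to study drug".

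The irAE definition in Section 6.2.1 matches the longer window: "IrAEs include events, regardless of causality, occurring within 100 days of the last dose". Section 7.2.1 promises separate irAE tables on that definition, by grade, with counts, percentages and 95% CIs.

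A related rule says which serious or reportable events are followed until they resolve or stabilize. Section 6.8.1, the synopsis (Study Procedures) and footnote 31 of both schedules give events "occurring during treatment or starting within 30 days of last study drug". Section 3.1.3 has the same rule with 100 days (nivolumab) and 90 days (ipilimumab).

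**The concern.** Sections 8.1 and 8.3 ask for all events to day 100/90, while 8.4, the section 8.1 points to for reporting, stops general recording and reporting at day 30. A site can follow either and believe itself compliant. If sites differ from the longer rule in practice, the safety data set will depend on which section staff happened to read.

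This matters because safety and tolerability are part of the surgical cohort's primary objective and a secondary objective in the main cohort, and because the protocol itself cites delayed immune-related toxicity as the reason for post-drug visits. Two planned outputs depend on the longer window: the sponsor's SAE reporting to BMS and the any-causality irAE table.

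**Working it through.** No sample size, power or type I error is involved. The check sets the rules side by side and then subtracts.

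**1. Windows as written**

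| Place | Governs | Limit after treatment | Events |
|---|---|---|---|
| 8.4 | recording and reporting | 30 days | all; later only SAEs or AEs of concern believed related |
| 8.4.1 | sending to sponsor | after 30 days | only related SAEs or AEs of concern |
| 8.1, 8.3 | reporting, recording | 100 / 90 days | all, related or not |
| Footnote 11, both schedules | monitoring | 100 / 90 days | all |
| 8.4.5 | sponsor to BMS | 100 / 90 days | SAEs, related or not |
| 6.2.1 | irAE definition | 100 days | regardless of causality |
| Synopsis, 6.8.1, footnote 31 of both schedules | follow to resolution | onset within 30 days | serious or reportable |
| 3.1.3 | follow to resolution | onset within 100 / 90 days | serious or reportable |

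**2. Can the texts be read together?** Treating 8.3 as recording and 8.4 as reporting does not work, because 8.4 limits recording too. Letting the longer rule prevail does not work either: there is no precedence clause, and 8.1 routes its 100/90-day duty through 8.4.

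**3. Size of the gap.** Gap = longer window − 30 days.
- Nivolumab: 100 − 30 = 70 days (70/100 = 70% of the window).
- Ipilimumab: 90 − 30 = 60 days (60/90 = 67% of the window).

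These overlap in the same patient and do not add. If both drugs stop on the same day, the exposed period is days 31 to 100, 70 days in all. The figures take the last dose of the named drug as the last study treatment. If other study treatment follows that dose, the 30-day clock starts later and the gap is shorter, hence 'up to'.

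**4. What is exposed on days 31–100 under 8.4 and 8.4.1**
- SAE judged related: kept.
- Non-serious event judged related and 'of concern' (a term left undefined): kept.
- Non-serious event judged related but not 'of concern': not required, though the irAE table needs it if it is an irAE.
- SAE judged unrelated: not sent to the sponsor under 8.4.1, but needed under 8.4.5.
- Non-serious irAE not attributed to treatment: not required, but needed under 6.2.1 and 7.2.1.

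**5. Do scheduled contacts close the gap?** Partly. The 90-day visit (Section 6.8.2) includes an AE assessment, but its window is 90 ± 14, that is, days 76 to 104, so it can fall 100 − 76 = 24 days before day 100. The three-monthly contacts that follow (Section 6.8.3) ask only about treatment-related toxicity.

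**6. Linked inconsistency.** Non-endocrine irAEs count only if the patient received immunosuppressive medication. Section 4.3.1 ends concomitant treatment at 30 days, except for therapy started in follow-up for a study-drug-related AE. Footnote 10 of both schedules records it to the 90-day visit. A late, unattributed event treated with immunosuppression could therefore lack the medication record that makes it an irAE.

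**The case against.** The strongest reply is that the protocol already demands the data. Sections 8.1, 8.3 and 8.4.5 all require 100/90 days regardless of relationship, and 7.2.1 separately requires irAEs as defined in 6.2.1 to be collected. Section 8.4 also requires investigators and sponsor to meet the timelines of the bodies they answer to, and it sends fatal and life-threatening events to the sponsor with no 30-day limit. Sponsor and principal investigator are one role, and one study site is named. Relatedness needs only a reasonable possibility (8.2.2), so most genuine late irAEs would be judged related and, if serious or of concern, still reported. Much of this stands, and it rules out several stronger readings that a reader might infer:

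- That the sponsor cannot meet its SAE duty, or that the irAE table cannot be built. Both hold only if a site follows 8.4/8.4.1 in preference to 8.1/8.3.
- That late immune toxicity is lost generally. Related SAEs and AEs of concern are retained.
- That the synopsis, 6.8.1 and footnote 31 end AE recording at day 30. They say which events are followed to resolution. Only 8.4 limits recording, and only 8.4.1 restricts what reaches the sponsor.
- That the stopping rules are undermined. The Bayesian rule (3.5.1) and the CNS interim rule (3.5.2) count only related events. What remains is a late, related, non-serious grade 3 event that nobody calls 'of concern'.

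The reply does not remove the contradiction. Section 8.4.1 still restricts what reaches the sponsor, 8.1 still defers to 8.4, and the two sets of rules cannot both be followed for an unrelated SAE on, say, day 60.

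**Conclusion.** The inconsistency is real, is in the current text, and should be corrected. Its effect is conditional. If sites apply 8.4 and 8.4.1, unrelated SAEs, and irAEs that are unattributed or neither serious nor of concern, may go uncollected for up to 70 days after the last nivolumab dose or 60 days after the last ipilimumab dose, and the irAE table would be understated to that extent. If sites apply 8.1 and 8.3, the all-AE shortfall created by the 30-day rule disappears, apart from the contact-timing and concomitant-treatment points above. The size is in days of risk time, not events: the documents give no late-event rate from which to estimate how many would be lost. The effect on the stopping rules is marginal at most.

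**What to change.** 1. In 8.4 and 8.4.1, replace the 30-day limit and the related-only filter with the 100/90-day minimum, regardless of relationship, already in 8.1, 8.3 and 8.4.5.
2. In the synopsis, 6.8.1 and footnote 31 of both schedules, align the follow-to-resolution window with Section 3.1.3.
3. Have a contact on or after day 100 ask about all AEs up to day 100, not only related ones. An existing three-monthly contact can serve, so no new visit is needed.
4. Reconcile the concomitant-treatment window in 4.3.1 with footnote 10 of both schedules, so that immunosuppressive use is recorded for as long as irAEs are counted.

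The cost is mainly an amendment to wording, plus one broader question at an existing contact and slightly more AE and medication recording. Section 8.3 already requires the AE part.

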### **For Narrative Reports of Safety Events**

If the report is supplied as a narrative, the minimum necessary information to be provided at the time of the initial report includes:

CONFIDENTIAL

This material is the property of the NYU School of Medicine. Do not disclose or use except as authorized in writing by the study sponsor

- Study identifier
- Study Center
- Subject number
- A description of the event
- Date of onset
- Current status
- Whether study treatment was discontinued
- The reason why the event is classified as serious
- Investigator assessment of the association between the event and study treatment

#### **8.4.1 Investigator Reporting: Notifying the Study Sponsor, NYUSoM IRB, Perlmutter Cancer Center Clinical Trials Office (PCC CTO), and BMS**

The following describes events that must be reported to the study **Sponsor** in an expedited fashion.

##### **Initial Report: within 24 hours of awareness of the event:**

The following events must be reported to the study sponsor by telephone within 24 hours of awareness of the event:

- Unanticipated problems related to study participation,
- Serious adverse events, regardless of whether they are unexpected.
- Overdose of Study Drug, defined in Section 8.1.
- Pregnancy: Although pregnancy is not considered an AE, it is the responsibility of the investigator to report to the Sponsor (or designee), by telephone within 24 hours of identification, any pregnancy occurring in a female subject or female partner of a male subject, during the study or within 5 months after the last dose of study drug for a female subject or within 7 months after the last dose of study drug for a male subject. Any complication of pregnancy affecting a female subject or female partner of a male subject, and/or fetus and/or newborn must be reported as an SAE. All pregnancy outcomes will be followed as described in Section 8.1. Pregnancies must also be reported on a Pregnancy Surveillance Form to BMS immediately as described in Section 8.1.
- Exposure during Pregnancy or Breastfeeding (even if not associated with an adverse event)
- Occupational exposure (even if not associated with an adverse event)
- Potential drug-induced liver injury (DILI): These events are considered important medical events and should be reported as SAEs. See Section 8.1 for DILI definition.

In the event the investigator is informed of an SAE that occurs after 30 days after the last dose of study treatment, only those SAEs or other AEs of concern deemed by the investigator to be related to study treatment will be reported to the sponsor. The investigator should make every effort to obtain follow-up information on the outcome of a treatment-related SAE until the event is considered chronic and/or stable.

Additionally, an **FDA Form 3500 (MEDWATCH Form)** must be completed by the investigator and faxed to the study **Sponsor/Overall PI** within 24 hours. The investigator shall maintain a copy of the MEDWATCH Form on file at the study site or can be obtained from the FDA website:  
<http://www.fda.gov/safety/medwatch/howtoreport/downloadforms/default.htm>.

